## **Inclusion/Exclusion Criteria**

Inclusion Criteria:

- (1) Age  $\geq$  50 years
- (2) Knee Pain plus ACR Criteria for Knee Osteoarthritis
- (3) BMI =  $27 \ge kg/m^2$

# Exclusion Criteria:

- 1. Significant co-morbid disease that would threaten safety or impair ability to participate in interventions or testing (Method: Medical history; medications; physical exam; telephone pre-screen; risk stratification)
  - a. Blindness
  - b. Type 1 diabetes
  - c. History or symptoms of coronary artery disease or pulmonary disease with no medical clearance (symptoms include angina, unreasonable breathlessness, dizziness/fainting/blackouts)
  - d. Unable to walk without a device
  - e. Lower extremity fracture (within previous 3 months)
  - f. Joint Replacement (excluded if double KR or within previous 6 months)
  - g. Knee injection or surgery (within previous 3 months)
  - h. Lower extremity injury that affects activities of daily living
  - i. Bariatric Surgery
- 2. Not sufficiently overweight or obese,  $BMI < 27 \text{ kg/m}^2$  (Method: Ht/Wt)
- 3. Not having knee pain: (Method: <1 on the pain scale, WOMAC and Telephone Screen)
- 4. Inability to finish 18-month study or unlikely to be compliant (Method: Telephone Screen, Screening Interviews)
  - a. Planning to leave area > 2 month during the next 18 months
  - b. Unwilling to change eating or physical activity habits
  - c. Unwilling to attend exercise/diet sessions
  - d. Participating in another intervention study (only if the other study has requested they not be enrolled)
  - e. Living > 30 minutes from the intervention site
- 5. Age, age < 50 (Method: Telephone Screen & Demographics Forms)
- 6. Other conditions that may prohibit the effective delivery of the intervention (Method: Telephone Screen)
  - a. Unable to provide own transportation to exercise center
  - b. Unable to read or write, cannot speak or read English

## Randomization Procedures

We propose a stratified block randomization with block size unknown to investigators and staff will ensure equal accrual to each study arm. Prestratification will balance pretrial BMI values  $(27.0-34.9 \text{ kg/m}^2, 35.0-44.9 \text{ kg/m}^2, \geq 45 \text{ kg/m}^2)$  and gender, which could predict intervention effect and associations between secondary outcome variables. We will also use county as a fixed effect for randomization. A computer program will randomize participants into the 2 groups, verify eligibility, and provide identification number and intervention assignment. This system worked very successfully in the IDEA study.

### **Interventions**

### Diet-induced weight loss plus exercise

#### Months 0 -6

There will be two individual sessions per month and 2 group sessions per month for the first 6 months. The behavioral sessions will focus on awareness of changing eating habits to lower caloric intake. Educational content information regarding what food changes to make, how to make them, and why they are important will be clearly explained and discussed with participants and significant others. Each group session will include problem solving, review of a specific food topic, and tasting of several well-balanced, low-fat, nutritious foods prepared with widely available ingredients. During the individual sessions, the counselor will review individual progress, solve problems, answer questions, and set goals. During the initial individual session, the nutrition counselor will give the participant a weight history background questionnaire. The major emphasis for Period 1 is to enhance participant awareness of the importance and the need to change eating habits, i.e. lower caloric intake for weight loss. Each participant should be given the opportunity to practice skills using goal setting in a stepwise approach. Participants will follow a weekly menu plan which will incorporate meal replacements into their diet plan. Lean Shakes, a General Nutrition Center (GNC), product will be the meal replacement used. Participants may replace the Lean Shakes with a healthy, low-calorie meal of their choice, such as Lean Cuisine. Motivation and encouragement through the combined efforts of the nutrition counselor, the participant, significant others and the nutrition staff will enhance adherence.

#### Months 7-12

In period 2 participants will focus on continued weight loss to reach the study weight loss goal of 10% of baseline weight. Participants will attend one group and one individual session per month. Once the weight loss goal is achieved an individual may either begin weight maintenance, or they may continue to lose additional weight using safe and healthy nutrition practices. Participants will follow a weekly menu plan with recipes using traditional foods and the option to incorporate meal replacements. The traditional meals will contain 400-600 kcals, be low in fat and added sugars, and high in vegetables, fruits, and whole grains. Snacks may be a bar, fruit, or vegetable providing ~100-120 kcals. Daily caloric intake for each participant will be adjusted to his or her rate of weight change. Each group will be encouraged to take a daily multivitamin/mineral supplement containing no more than 100% of the Dietary Reference Intake for any particular nutrient. As fewer meal replacements are consumed, intervention staff will assist in developing meal plans to provide the prescribed macronutrient-balanced energy intake.

### Months 13-18

Period 3 will emphasize weight management over time, with 1 monthly individual contact. Weight loss can continue throughout the intervention, provided the participant wants to and has not reached a level associated with health hazards; i.e. a 20% body weight loss at 6 months or >30% at 12 months. Participants will continue to follow a

weekly menu plan with recipes using traditional foods and the option to incorporate meal replacements.

The exercise intervention will cover an 18-month period. The exercise program will consist of a 15-minute aerobic phase, a 20-minute strength-training phase, a second 15-minute aerobic phase, and a 10-minute cool-down phase. These sixty-minute exercise sessions will be conducted three days per week (two days/week will be center based). Each participant will be prescribed an individual walking prescription by the exercise leader, which will be adjusted accordingly, as each participant progresses throughout the 18 months. The exercise will be of moderate intensity. Alternate forms of aerobic exercise, such as but not limited to stationary bike, elliptical trainer, or treadmill walking, can be used in place of over-ground walking. This choice could be based on participant preference, the limitations of the exercise facility, or the participant's pain level. To motivate participants to be physically active intervention staff will plan an optional fun walk. The walk will take place at Wake Forest University. Participants do not have to participate in the walk in order to be in the study. If a participant chooses to participate in the walk they will be asked to sign a waiver.

Intervention Locations: *Forsyth County:* The diet and exercise classes will be offered at a number of sites within Winston-Salem. Participants will be allowed to pick the location that is most convenient for them to attend. Classes will take place at the Clinical Research Center on the Wake Forest University Campus, at St. Peter's World Outreach Center, and at Smiley's Fitness. *Haywood County:* The diet and exercise classes will be held at the Haywood Regional Health & Fitness Center in Waynesville, NC. *Johnston County:* The diet and exercise classes will be held at the Clayton Community Center and the Johnston Medical Mall. Participants will also be allowed to exercise outdoors at the intervention sites when the weather permits. Staff will schedule set times when outdoor walking will be allowed.

The following measures will be taken in the event participants are unable to come into the facility:

- Virtual Sessions Participants will be given the option to attend virtual exercise and diet classes. Intervention classes will be taught via Zoom. Participants will be provided with the class login information. The group and diet exercise sessions will be recorded and posted to our study Facebook page as well as sent to participants who are unable to attend the live sessions. Recordings will be edited so that only the class exercise and diet instruction can be viewed (beginning and end of the session as participants log in and out will be cut out of the video). As a security measure the virtual classes will be locked after 10 minutes so that no others can join the class. Additionally participants will not be given access to record the session. Individual sessions will also be conducted via Zoom.
- 2. Phone Sessions Staff will call participants to deliver the diet group and individual session content. All participants have previously been provided with at home exercise manuals. Staff will also use this time to review our non-facility-based exercise plans.

3. Email Sessions – Participants may also choose to receive the diet group and individual session content via email. All participants have previously been provided with at home exercise manuals. Staff will also use this time to review our non-facility-based exercise plans.

All intervention staff in the WE-CAN study will be CPR certified. The exercise coordinator, who is part of the coordinating center and is responsible for maintaining exercise protocol congruity between the intervention sites, will train and supervise the intervention staff. Intervention staff will meet monthly with the exercise coordinator to discuss any potential problems, risks, and concerns that have risen. AEDs will be available at each location. Emergency drills will be performed monthly in addition the AED will be checked monthly. The clinical research center (Forsyth), Johnston Medical Mall (Johnston), and the Haywood Regional Health and Fitness Center (Haywood) also house cardiac rehabilitation programs and will also have crash carts available.

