## Study Design

We will randomize 820 overweight and obese (BMI  $27 \ge kg/m^2$ ), adults age  $\ge 50$  yrs knee OA into one of 2 groups: an intensive dietary restriction-plus-exercise (D+E) group or an attention control (nutrition and health) group. Persons who have begun screening once we hit our overall recruitment goal of 820 will be allowed to complete the screening process therefore up to 840 persons may be enrolled into the study. Forsyth, Johnston, and Haywood Counties' recruitment goals are 420, 210, and 210, (total 840) respectively. Our minimum weight-loss goal for the weight-loss group will be 10% of body weight. The exercise intervention will meet 3 days/wk at the clinical site. The intervention will be comprised of both aerobic and strength training exercises. When participants are unable to come into the facility for intervention, sessions will be conducted via phone or through video conferencing. The nutrition and health group will meet 5 times over an 18 month period and receive a combination of webinars, video messages, text messages, emails (via personal email or Facebook), phone calls, and mailings for the remaining months. Participants will be allowed to choose their preferred method.

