## 1) Recruitment

- a. The study has created digital ads (submitted with this amendment) that will be used in Facebook ads. Ads posted will be pop up ads.
- 2) Study Notifications & Contact Method
  - a. The study will set up a Facebook page in which participants will be given the link (usage will not be required but will be an additional method that participants can

use to contact study staff or find out study information). A description of this usage is listed below.

- i. Study info such as press releases, news articles, manuscripts will be posted to the study Facebook page. This information will also be provided in study newsletters (for those not on Facebook).
- ii. Information regarding site closings (such as in the event of inclement weather or holidays) or intervention materials (group intervention classes) will be posted on the Facebook page. Please note all participants will be given information regarding holiday closings and weather policies in their intervention classes. A study phone number will be given to each participant which will be updated in the event of a closing. It will not be necessary to check Facebook to learn of a study closing.
- iii. Participants in the study will also be able to use Facebook as a means of contacting the staff by sending a private message (email) to the staff. This method may be useful to the nutrition and health group in which participants will be given a choice to their preferred method of contact (email, phone, Facebook private message).
- 3) Participant Posting
  - a. The study will set up its account as a page therefore it will not be a private group. Therefore the study will only post study information (press releases, articles, etc.) and site information. We will not post pictures or study participant information. However participants whom are on Facebook will be allowed to post to the study page. All posts will be reviewed by the study staff to ensure no other participants are identified as being a part of the study.

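### Recordings of the diet-and-exercise classes go on an open study Facebook page whose link is not limited by arm, and the plan's own posting rules disagree on whether they belong there

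*Combined protocol and SAP*

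**What the plan says.** **Recordings.** The measures for participants who cannot come to the facility (end of the D+E intervention description, Virtual Sessions item) state: "The group and diet exercise sessions will be recorded and posted to our study Facebook page". Recordings are edited down to the instruction itself and are also sent directly to those who miss the live class. The live class is locked after 10 minutes, as a security measure.

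**The page.** Usage of Facebook, item 2.a: "The study will set up a Facebook page in which participants will be given the link". No arm is named, and the same item adds that "usage will not be required". Item 3.a: "The study will set up its account as a page therefore it will not be a private group".

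**What the page may carry.** Item 2.a.ii: "Information regarding site closings (such as in the event of inclement weather or holidays) or intervention materials (group intervention classes) will be posted". Item 3.a: "Therefore the study will only post study information (press releases, articles, etc.) and site information".

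**Controls and Facebook.** Study Design lists "emails (via personal email or Facebook") among the contact routes for the nutrition and health group. Of private messaging, item 2.a.iii says: "This method may be useful to the nutrition and health group".

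**Planned exchange of content.** The 18-month follow-up visit description gives each group a mini session on the other group's program at the end of the study.

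**The concern.** The trial estimates the difference between D+E and an attention control. The control meetings cover topics such as foot care, general nutrition, medications and sleep, and no exercise classes are listed for that arm. The recordings therefore carry part of what separates the arms. Placing them where both arms can see them opens a route for contamination that the design does not need.

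Analysis is by intention to treat, so a control who followed the recordings would still be counted as a control. Any resulting benefit would shrink the 18-month WOMAC pain contrast. Nothing in the plan suggests an effect in the other direction.

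There is also a practical problem. Staff who follow the Virtual Sessions item would post recordings. Staff who follow item 3.a of the Facebook section would not.

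**Working it through.** **Step 1. Who can see the recordings.**
- Where they are posted: the study Facebook page (Virtual Sessions).
- Type of page: not a private group (item 3.a).
- Who gets the link: participants, with no restriction by arm (item 2.a).
- Limit on who views a posted recording: none stated.

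Together these give controls access before 18 months. They do not show that any control would watch.

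**Step 2. Whether the posting rules agree.** Item 2.a.ii can be parsed in two ways.

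| Reading of item 2.a.ii | Virtual Sessions | Item 2.a.ii | Item 3.a |
|---|---|---|---|
| Class materials themselves may be posted | posts recordings | allows it | does not list it |
| Only information about closings and class materials is posted | posts recordings | notices only | does not list it |

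On the first reading, item 2.a.ii supports Virtual Sessions and both conflict with the restrictive sentence in item 3.a. On the second, Virtual Sessions alone conflicts with item 3.a. The sentence in item 3.a needs reconciling either way.

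**Step 3. The plan's power.** Inputs from Primary Outcomes, Aim 1: 410 per group, 80% retention, SD 3.50, correlation 0.4, difference 0.887, two-sided 0.05.
- Analyzed per arm: 410 × 0.80 = 328.
- Conditional SD: √(1 − 0.4²) × 3.50 = 3.208.
- Standard error: 3.208 × √(2/328) = 0.2505.
- Standardized difference: 0.887 / 0.2505 = 3.54.
- Power from the noncentral t distribution: 94.2%. The stated 94% is reproduced.

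**Step 4. Sensitivity to dilution.** The documents give no viewing figure, so every dilution input here is assumed. Let f = (share of controls following the recordings) × (share of the D+E benefit the recordings give) × (share of the 18 months exposed). The diluted difference is 0.887 × (1 − f).

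| Assumed inputs | f | Difference | Power |
|---|---|---|---|
| 5% × 10% × 1/3 | 0.17% | 0.886 | 94.2% |
| 10% × 20% × 1/3 | 0.67% | 0.881 | 94.0% |
| 5% × 20% × 1 | 1% | 0.878 | 93.8% |
| 10% × 20% × 1 | 2% | 0.869 | 93.4% |
| 10% × 50% × 1 | 5% | 0.843 | 91.9% |
| set directly | 10% | 0.798 | 88.9% |
| set directly | 20% | 0.710 | 80.8% |

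Power falls below 90% only when f exceeds 8.3%. At an assumed 20% share of benefit and full exposure, that needs 8.3% / 20%, or about 42% of controls, following the recordings for all 18 months. The last two rows mark the scale and are not expectations.

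**The case against.** The strongest reply is that this is a pragmatic trial, posting is a contingency, and nothing shows that controls would use the recordings. The recordings leave out individual counseling, meal replacements and supervised center-based exercise. In months 13 to 18 the diet program names only a monthly individual contact. The arms already share a venue, since one site in Winston-Salem hosts both D+E classes and control meetings. The planning difference was set against an exercise-only comparator with some attenuation, so subtracting a further loss may count the same thing twice. All of this stands, and it is why the point is minor.

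Four stronger readings are tempting, but the documents do not support them.

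- **The Facebook section flatly forbids the recordings.** It does not. Item 2.a.ii can fairly be read as permitting class materials. Item 3.a sits under Participant Posting beside privacy rules and has an open-ended list. The clear clash is with its restrictive wording only.
- **Controls are expected to use the page.** Study Design offers Facebook as one way of receiving messages, and item 2.a.iii describes one-to-one contact that might be useful. Page use is optional, and the Nutrition & Health Intervention section does not mention Facebook.
- **The lock on live classes shows an intention to keep controls out, which the posting then defeats.** The lock is described as a security measure. Nothing ties it to contamination.
- **The mini session implies that content is otherwise withheld from the other arm.** The plan does not say so. It fixes only when a deliberate exchange takes place.

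The reply does not remove the access itself, the lack of any need for it, or the mismatch in the posting rules.

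**Conclusion.** The point holds as a minor one. The plan puts active-arm class recordings on an open page whose link both arms may receive, and its content rules for that page do not agree. Both can be avoided.

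The size of any effect is unknown and probably small. Its direction would be toward no difference in 18-month WOMAC pain. With an assumed dilution of up to 5%, planned power stays at about 92% to 94%. That range rests on the plan's own variance, correlation and retention figures and on a simple multiplicative dilution for which the documents offer no data.

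A reader might infer that the primary comparison is in danger. The documents do not support that: a serious loss would need uptake and benefit among controls far beyond anything they suggest. The case for change rests on unnecessary access and inconsistent instructions, not on lost power.

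**What to change.** **Virtual Sessions item.** Replace posting on the study page with restricted delivery. Suggested wording: *Recordings will be sent only to participants in the diet and exercise group, by direct link or through a private group limited to that arm, and will not be placed on the open study page.* Direct sending to those who miss a class is already planned, so no new system is needed.

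**Usage of Facebook, item 2.a.ii.** Limit class-related posts to schedule and closing notices, so that it agrees with item 3.a.

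**Cost.** Wording changes in two sections and a change of channel. Sample size and analysis are unaffected. The downside is that D+E participants must open a sent link or join a private group. They keep the recordings, so support for adherence when sites are inaccessible is retained.

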## Nutrition & Health Intervention

The nutrition and health (attention control) intervention will cover an 18-month period. There will be five total face to face group meetings over the 18 months, with one meeting each at months 1, 3, 6, 9, and 15; and during the other months (months 2, 4-5, 7-8, 10-14, 16-18) participants will receive a combination of informational packets, webinars, text messages, and emails. Participants will be able to select their preferred method. Each group meeting will last approximately one hour and will be held at St. Peter's World Outreach Center and at Senior Services in Winston-Salem, NC. The sessions will be interactive and will provide useful information on such topics as proper foot care, general nutrition, health behaviors, management of medications, and sleep practices. The Community Advisory Board will give input on the class sessions.

Experts across a broad range of relevant topics that are of interest to older adults will provide information via information packets, webinars, text messages or emails. These monthly contacts and email blasts will keep the participants in the nutrition and health group engaged in the WE-CAN study and will increase adherence to the group sessions and the testing visits.

Participants in both interventions will be provided with items with the study logo such as t-shirts and tote bags to promote group bonding and study adherence. Additionally, giftcards will be raffled at various class sessions. In order to better balance the amount of money spent on the two groups participants in the Nutrition & Health group will receive a \$100 (gift cards) for completing the testing appointments. They will be given \$25 at 6 months and \$75 at 18 months. At the 12-month testing appointments the participants will receive an incentive with the study logo. Participants in the Diet & Exercise group will be receiving meal replacements for the first year of the study.

### Procedures-Screening and Follow-up Visits.

Measurements	PSV	SV1	FU6	FU12	FU18	Explanation
	1	1	Ċ	Questionna	ires	-
Informed Consent		х				
Eligibility Questionnaire	х					To determine eligibility
Medical History/Med History FU	хс	х	х	x	x	For eligibility and to document changes in health
Risk Stratification	хс	х				Used to screen cardiovascular risk
Comorbidities Questionnaire		х		х	х	
Randomization		х				
WOMAC		х	x	x	x	Pain is primary and function secondary outcomes. Will be taken from the KOOS
Knee Injury and Osteoarthritis Outcome Score (KOOS)		x	х	x	х	Assesses patient's opinion about their knee and associated problems
PASE scale		х	х	х	х	Physical Activity Scale for the Elderly
MOCA		х			х	Montreal Cognitive Assessment
EuroQol Quality of Life(EQ5D)		х	х	х	Х	Quality of life measure
Resource Utilization		x	х	x	x	Visits to clinicians, tests, medications, injections, surgery, alternative therapies
Work Productivity and Activity Impairment Index		х	х	x	x	assesses absenteeism and presenteeism
DHQ II		х	х	х	х	NIH Diet History Questionnaire
SF-36		х	х	х	х	Health related quality of life (physical, mental)
Health Literacy		х	Х	х	х	
Adherence Self Efficacy		x	х	x	x	Confidence in exercising at various intensities and frequencies
Adherence for Duration		Х	Х	х	х	Confidence in walking for different durations
Gait Efficacy		Х	Х	х	х	Confidence in completing tasks
Demographics		Х				
Medication form		х	х	х	х	Atherosclerosis Risk in Communities form
Weight Efficacy Questionnaire		х	х	х	х	Self-Efficacy for Weight Management
PANAS		х	х	x	х	Positive and Negative Affect Scale
SWL		х	х	x	х	Satisfaction with Life
Perceived Stress		х	х	х	х	Stress
Pain Catastrophizing Scale		х	х	Х	х	Catastrophizing
Intermittent and Constant Osteoarthritis Pain (ICOAP)		x	х	x	Х	Intermittent and Constant Pain
CES-D		х	х	x	Х	Depression
Transition Questionnaire			х	х	Х	Knee pain
Adverse Events			х	Х	Х	Also collected as they occur
	-		sical Perf	ormance T	ests/Knee E	
height	XC	х				To determine BMI
weight	XC	х	х	х	Х	To determine BMI
Knee exam		х				To determine eligibility
6 minute walk		х	х		X	Measure of mobility
Expanded Short Physical		х	х	х	Х	Gait speed, sit to stand, balance tests; predicts
Performance Battery (SPPB)						disability
GaitRite		X	X	X	X	mobility measures
Stair Climb xc = brief screen by self-report, P		Х	х	х	Х	mobility measure

Procedures-Screening and Follow-up Visits.

Prescreening visit (PSV). Individuals who contact our recruitment office in response to advertising will be asked a series of brief questions that focus on major eligibility criteria. A screening visit appointment will be made for participants who meet major eligibility criteria. A medical history form and a medication form will be mailed to the participants for them to complete. If participants are unable to come in for testing appointments research staff will call participants via Webex to collect study data (participants can choose whether to attend virtually or only via phone). Staff will use a HIPPA compliant version of Webex (set up by Wake

Forest University). To reduce participant burden only the following questionnaires will be collected: cost effectiveness questionnaires, WOMAC, KOOS, Physical Activity Scale for the Elderly (PASE), Health-Related Quality of Life (HRQL), and efficacy measures. In the event participants do not wish to conduct a phone or virtual session a questionnaire packet will be mailed to participants to complete and return. The webex testing session will last approximately 1 hour.

Screening Visit One (SV1) Individuals will come to Worrell Professional Building on the campus at Wake Forest University. SV1 includes an explanation of the study and obtaining informed consent. Other assessments include medical history and medication use (previously mailed), cardiovascular risk, height and weight (to calculate BMI), hip/waist circumference measurements, blood pressure, and a knee exam. The MOCA & CES-D will be administered. The following questionnaires will be given: demographics, cost effectiveness questionnaires, WOMAC, KOOS, Physical Activity Scale for the Elderly (PASE), Health-Related Quality of Life (HRQL), dietary intake questionnaires, health literacy, perceived stress, pain catastrophizing, and efficacy measures. Physical performance measures include the SPPB, 6 minute walk, GaitRite, and stair climb. This screening visit will last approximately 3 - 4 hours.

Randomization Visit (RV) Individuals will come to Worrell Professional Building on the campus at Wake Forest University. At the RV an orientation to the group will be done.

6-month Follow-up Data Collection Visit (FU6): Participants will return to Worrell Professional Building to repeat all measures collected at baseline (minus the MOCA, knee exam, and demographics). The testing session will last approximately 2.5 - 3.5 hours.

12-month Follow-up Data Collection Visit (FU12): Participants will return to Worrell Professional Building to repeat all measures collected at baseline (minus the knee exam and demographics). The testing session will last approximately 2.5 - 3.5 hours.

18-month Follow-up Data Collection Visit (FU18): Participants will return to Worrell Professional Building to repeat all measures collected at baseline (minus the knee exam and demographics). The testing session will last approximately 2.5 - 3.5 hours. At the end of 18 months the participants will have a mini session on what the other group received.

